Study Title: Group Cognitive Behavioral Therapy for Anger and Aggression in Veterans with PTSD

Clinical Trials Identifier: NCT02233517

Protocol and Statistical Analysis Plan

Research Protocol

Group Cognitive Behavioral Therapy for Anger and Aggression in Veterans with PTSD

Summary & Purpose

Posttraumatic stress disorder (PTSD) robustly predicts anger and aggression (Olatunji, Ciesielski, & Tolin, 2010), and U.S. Iraq/Afghanistan-era Veterans report that controlling anger and aggressive urges are primary readjustment concerns (Sayer et al., 2010). Anger interferes with recovery in therapy for PTSD (Foa, Riggs, Massie, & Yarczower, 1995; Forbes et al., 2008); as such, the DOD/VA Clinical Guidelines for the Treatment of PTSD recommend that Veterans with anger problems be specifically referred to anger management treatment. While anger management groups are offered at most VA hospitals, CBOCs, and Vet Centers, the virtual absence of established empirically supported treatments for PTSD-related anger and aggression leaves VA clinicians unclear as to how to most effectively treat these pervasive and disabling problems ([name] et al., 2010).

The proposed research project is a pilot study of the efficacy of Cognitive-Behavioral Therapy for Anger and Aggression in Combat Veterans with PTSD (CBT-A). CBT-A is a 12-week manualized group treatment protocol that is grounded in current research, and that has been designed to specifically address the cognitive, affective, and behavioral components of combat PTSD-related aggression. Specifically, this project will be a pilot 2-arm, randomized clinical trial comparing group CBT-A to group Present Centered Therapy (PCT), an active therapy control condition commonly used in PTSD efficacy studies.

The proposed pilot study has two Specific Aims: 1) to evaluate the feasibility of a full-scale RCT evaluating the efficacy of Cognitive Behavioral Therapy for Anger and Aggression (CBT-A) in combat Veterans with PTSD, and 2) to characterize the differences in effects of CBT-A and PCT on anger, aggression, and anger/aggression related functional impairment and quality of life in combat Veterans with PTSD. Specific objectives have been identified for each of these aims.

Aim 1: Evaluate study feasibility and treatment delivery procedures of a RCT comparing CBT-A to a PCT comparison condition.

Specific Objectives for Aim 1:

1. *Evaluate response rate to recruitment efforts and rate of accrual into the study.*

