2. *Evaluate group drop-out rates.*
3. *Evaluate participant retention through the 6-month follow-up assessment.*
4. *Evaluate success of the randomization procedure, including the association of potential stratification variables with feasibility variables and treatment outcome.*
5. *Evaluate therapist treatment fidelity.*
6. *Assess adverse event frequency and severity.*
7. *Assess treatment adherence and participant engagement in treatment.*

Aim 2: Characterize the difference between the CBT-A intervention and the PCT comparison condition in effects on PTSD-related anger and aggression, anger and aggression-related functional impairments, and quality of life.

Specific Objectives for Aim 2:

1. *Examine the effects of the CBT-A intervention on reducing aggression and violence.*
2. *Examine the effects of CBT-A on managing PTSD-related anger; diminishing the negative impact of anger and aggression on functional life domains; and diminishing the negative impact of anger and aggression on quality of life.*
3. *Other outcomes of interest include: changes in PTSD symptoms and incidence and severity of substance misuse.*

[figure not shown]
Background and Significance

Anger and aggression are positively associated with PTSD with medium to large effect sizes, particularly in military and Veteran samples (Andrews & Brewin, 2012; Orth & Wieland, 2006), and U.S. Iraq and Afghanistan-era combat Veterans report controlling anger and aggressive urges as primary readjustment concerns. In a sample of 754 help-seeking Iraq and Afghanistan combat Veterans, 57% reported problems

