Though anger and aggression lead to functional impairment and diminished quality of life in Veterans with PTSD, they may also play an important role in how Veterans cope with their PTSD symptoms. A core facet of PTSD is avoidance of others because of the possibility of encountering conflict; feeling vulnerable; or experiencing sadness, guilt, or fear. As such, Veterans with PTSD may use anger or aggression 1) to distract themselves from other negative affect such as fear, guilt, sadness, or vulnerability by fostering a sense of power and control (Foa et al., 1995; Gerlock, 1994); 2) to control others' behavior through instilling fear; and 3) to keep others at bay, allowing for the use of behavioral and emotional avoidance to cope. Because these behaviors are used by Veterans with PTSD to distance themselves from others, it may be difficult for them to accurately report the negative effects they are having on those closest to them. To accurately measure the effect of the intervention on functioning, therefore, it is important to collect information from collateral sources. Unfortunately the few studies of anger and aggression interventions in Veteran have typically not incorporated collateral reports of anger and aggression, leaving a significant gap in our ability to accurately evaluate the effectiveness of the intervention.

The proposed study is a 2-arm, randomized clinical trial comparing group CBT-A to group PCT. Thirty-six (12 female, 24 male) eligible Veterans who agree to participate will be randomized to one of two group conditions: CBT-A (n = 18; 6 female, 12 male) or PCT (n = 18; 6 female; 12 male). Each of the 3 CBT-A and 3 PCT groups will consist of 5-6 members.

Please note that in some correspondence with participants and/or recruitment materials, this study may be referred to by the acronym **CALM**, Cognitive Behavioral Therapy for Aggression and Anger Level Management.

Methods

Selection of Subjects

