There is a subset of Veterans with PTSD who are unlikely to voluntarily seek treatment in the VA (Spoont et al., 2014). Reaching this hidden population of Veterans who do not seek treatment in order to provide them treatment for anger management is an important goal. In order to reach Veterans who may not be enrolled for care in the VA system, we will plan to use a recruitment method referred to as respondent-driven sampling, or "seed recruitment" ([name]., personal communication). Seed recruitment is suitable for sampling "hidden populations" of participants who are best known by their own peers (Heckathorn, 1997). It includes providing incentives to participants for referral of other eligible participants. In our model, each participant, or seed, will receive two coupons to recruit other Veterans in his/her social networks. The recruitment coupons will provide a brief description of the survey and a phone number for contacting the study coordinator. The coupon will be marked with a unique identification number (not the study identification number) so that when the coupons are returned to us, the ID number can be used to provide a small payment (\$5) to the participant who made the referral. The key connecting the participant's study ID number with the seed ID number will be kept in a database separate from other PHI, creating two layers of separation between the seed ID and the already-participating Veterans' identifying information. Any Veteran who does not wish to recruit in this manner will not be required to do so.

It is estimated that 60 potential participants (20 women, 40 men) will be consented and screened, and 36 will be randomized to a study condition. Considering drop-out rates in pilot groups of CBT-A, in studies in the

Traumatic Stress and Health Laboratory more broadly, and in previously published studies of anger management in Veterans, we will assume a 15% drop-out rate, for a final sample of 30 individuals with PTSD that will complete the interventions. Because the planned full RCT will employ an intent-to-treat analysis using a mixed-models repeated measures statistical approach, we will include all 36 randomized participants in all analyses.

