Any participant who cannot or chooses not to identify a collateral reporter to participate alongside him/her will still be allowed to participate in the other portions of the study. Once a collateral reporter has been identified by the participant (see Collateral Informant Contact Information Sheet), the study coordinator will contact him/her regarding participation in the study. He/she will be asked to attend an in-person session in which he/she will provide informed consent, sign HIPAA authorization, and complete study questionnaires. If the study coordinator is not able to reach the identified friend or family member, the participant may be asked to provide the name and contact information of another potential collateral reporter. If the family member or companion who consents in session one is unable to attend session two, the veteran will be asked to identify another family member or companion, who will be consented prior to beginning session two. Any time a collateral reporter chooses to withdraw from the study, this will not impact the participation of the main study

participant. The Traumatic Stress and Health Research Laboratory has extensive experience conducting studies asking veterans and their family members to describe violence and has had a very low rate of refusal to participate from family members.

Screening Procedures

Potential participants will undergo a brief telephone screen, followed by an in-person screening session at the Durham VA Medical Center (DVAMC). At the beginning of the in-person screening session participants will be provided with greater detail about the group requirements and procedures, as well as about randomization to one of the two treatment conditions. In an effort to diminish attrition rates, the screener will discuss with the participant his or her ability and willingness to adhere to the study conditions. The screener will encourage the participant to identify potential barriers to group attendance and treatment adherence, and will assist him or her in brainstorming solutions to these barriers.

Each potential participant will be administered the CAPS to evaluate for current PTSD; the SCID to assess for the presence of comorbid disorders; the Brief Traumatic Brain Injury Screen. Upon determination of eligibility, participants will complete the pre-intervention measures.

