In order to enhance participant retention during the 6-month follow-up period, we will use strategies recommended by Wisniewski and colleagues (Wisniewski et al., 2006). Specifically, we will maintain frequent participant contact throughout the evaluation period. For example, we will make intermittent phone calls to participants to check on their status, and, where relevant, send birthday and holiday cards and study newsletters to encourage a sense of community and ownership of the study. We will also employ methods we have successfully used in [name] large longitudinal study of Afghanistan/Iraq-era Veterans (i.e. [name], 2012), including mailing reminders 16 days after follow-up materials are sent either thanking them for participating in the assessment, or encouraging them to do so.

Please see Table 1 for timing of administration of all assessments.

Optimal randomization of participants to group would require us to enroll 12 eligible participants prior to group assignment, resulting in significant delays between screening and the initiation of treatment (Schnurr, Friedman, Lavori, & Hsieh, 2001). However, requiring participants to wait for several months between study enrollment and treatment for anger and aggression may be ethically questionable, and may also increase the likelihood that a high percentage would drop out of the study prior to the first session to seek treatment elsewhere. As a result, we will begin a group immediately upon enrollment of 6 participants, and will alternate the initiation of CBT-A and PCT groups through the implementation process. Participants will not be stratified to group in this pilot study. Instead, randomization effectiveness will be evaluated through an examination of pre-treatment variables including PTSD severity, anger severity, and level of aggression. If there is evidence of randomization failure, this will be addressed through the use of covariates in analyses of the pilot data, and

will be used to evaluate the need for alternative randomization procedure or the use of stratification variables in future studies (US Department of Veterans Affairs Office of Research & Development, NIMH, & DoD, 2008).

Measures

Demographic Information

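### The trial is called randomized, but the only allocation rule is alternation of CBT-A and PCT groups, with no random sequence, random first arm or concealment described

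*Combined protocol and SAP*

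**What the plan says.** Randomization is stated in several places:

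- Summary & Purpose: "this project will be a pilot 2-arm, randomized clinical trial comparing group CBT-A to group Present Centered Therapy (PCT".
- Design paragraph closing Background and Significance: "eligible Veterans who agree to participate will be randomized to one of two group conditions".
- Subject Recruitment: "36 will be randomized to a study condition".
- Screening Procedures, on what participants are told: "as well as about randomization to one of the two treatment conditions".
- Specific Objectives for Aim 1, objective 4: "Evaluate success of the randomization procedure".

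The method of assignment appears once, later in Screening Procedures. It opens with an ideal: "Optimal randomization of participants to group would require us to enroll 12 eligible participants prior to group assignment". That is set aside because the delay might be ethically doubtful and might lose participants. The rule adopted is "we will begin a group immediately upon enrollment of 6 participants, and will alternate the initiation of CBT-A and PCT groups". There is no stratification. As a safeguard, "randomization effectiveness will be evaluated through an examination of pre-treatment variables including PTSD severity, anger severity, and level of aggression", with covariates if a failure is seen, and the findings are to inform allocation in later studies.

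No section gives a random sequence, how the first arm is chosen, who assigns, or any concealment. The figures and appendices missing from the text are cited for other matters (the anger model, the timeline and payments, the recruitment letter, session content).

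**The concern.** If a group starts at the sixth enrolment, those six enter it together, and their arm depends on when they enrolled. Anyone who knows which arm started last can foresee the next one while still screening for it. Arms may also differ because they were filled in different periods. Randomization with concealment protects against the first problem, and a random order at least leaves the second to chance. Alternation does neither.

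Three things depend on the label. The β3 test and the effect size meant for sizing the full RCT would be read as randomized evidence. Objective 4 would report on a procedure that the protocol does not describe, and the full RCT could inherit it as tested. Participants are told of a randomization that the text does not contain.

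The stated reason does not require this rule. Not waiting for 12 enrolees justifies groups of six. It does not justify a fixed arm order, because drawing the order of the same six groups adds no wait.

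**Working it through.** **1. The plan's own figures.** Three CBT-A and three PCT groups of up to 6 give 6 × 6 = 36, or 18 per arm. With 15% drop-out, 36 × 0.85 = 30.6, stated as 30. Both reproduce. No sample size figure is in dispute.

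**2. Could the rule mean individual randomization?** Under simple 1:1 randomization, the chance that the first six enrolees all fall in one arm is 2 × 0.5⁶ = 3.1%. One arm would first reach six after 9.3 enrolments on average. A start at the sixth enrolment therefore means that the six are assigned as a block.

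**3. How many participants have a deducible arm?** Recruitment of Women gives one women's and two men's groups per arm, so two women's and four men's groups of 6.

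| Reading of the alternation | Deducible groups | Participants |
|---|---|---|
| Separate by sex, first arms unknown | 3 of 4 men's + 1 of 2 women's | 18 + 6 = 24 of 36 |
| One shared sequence, first arm unknown | 5 of 6 | 30 of 36 |
| First arm fixed in advance | 6 of 6 | 36 of 36 |

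The protocol does not say which applies. A shared sequence fits poorly: of the 15 possible positions of the two women's groups among six, 6 (40%) would put both in the same arm, contrary to one per arm.

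**4. Comparator.** With known totals, a random order within sex also leaves some groups deducible. The second women's group always is (6 participants). Among the men, the fourth group always is, and the third is in 2 of the 6 possible orders: (1 + 2/6) × 6 = 8. The average is 6 + 8 = 14 of 36. On the first reading, alternation therefore adds 24 − 14 = 10 participants.

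**5. Sensitivity of the baseline check.** The protocol plans an examination and names no test. Assume a two-sample t-test, two-sided 5%, 18 per arm, on measures taken before any group meets. For a true imbalance of 0.5 SD the noncentrality is 0.5 × √(18/2) = 1.5, which gives power 0.308. Power of 80% needs an imbalance of 0.96 SD.

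**The case against.** The protocol does not hide the compromise. It says a better procedure was set aside, gives an ethical and a retention reason, plans a baseline check with covariates, and will use the result in later designs. The list of variables to be compared is introduced as examples, so it can be extended. The aims are feasibility and characterization, and Power Analysis and Sample Size Determination already warns that pilot effect sizes are uncertain. Male recruitment is complete, so little of the allocation can still be changed. All of this stands, and it limits the seriousness of the point.

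It does not supply the missing property. The same paragraph still speaks of the effectiveness and failure of randomization, as though a random step remained. Covariates act only on what was measured, and confidence intervals cover sampling error only.

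A reader might infer that staff steered participants between arms. The documents do not support that. Eligibility rests largely on the CAPS, the SCID and a brain injury screen with record review. Expected medication instability leaves room for judgement, but the talk about willingness to adhere is an anti-attrition step and not a listed criterion. That groups fill strictly in enrolment order is also an inference from the start rule; session site may depend on space and preference, and the effect on membership is not stated.

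**Conclusion.** The point holds as a defect of description and design: a property claimed in several sections is absent from the only rule given, and objective 4 has no randomization procedure to evaluate. It should be fixed, but it does not undermine the pilot's feasibility purpose. The 24, 30 and 36 depend on unstated features of the alternation, and 24 should be read against 14. The 31% depends on the assumed test.

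Three further inferences are tempting and should not be drawn.

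- **Deployment criterion.** It was dropped for women during recruitment, so early women enrolees may cluster in one arm. That comes from filling groups in turn and would persist under a random draw of arm order. It is not evidence against alternation.
- **A numerical bias in the effect size.** Any figure needs an assumed imbalance, and the documents give none. Even under perfect individual randomization with 18 per arm, the standard error of a baseline difference is √(2/18) = 0.33 SD, so a difference of at least 0.5 SD arises by chance about 13% of the time.
- **Change-score against baseline-adjusted estimates.** Their difference equals (b − 1) times the observed baseline difference, where b is the slope of post-treatment on pre-treatment score. They differ under perfect randomization too, so a gap does not show that allocation failed.

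**What to change.** 1. **Groups not yet assigned** (at most the two women's groups). Draw the arm order at random and conceal it from screening staff until members are enrolled and pre-treatment measures are complete. State that the second women's group remains deducible. The draw reaches at most 6 of 36 participants, and none if the first women's group is already assigned.
2. **Groups already formed.** In Summary & Purpose, the design paragraph of Background and Significance, Subject Recruitment and Screening Procedures, replace the randomization wording with *allocated by alternation of groups*. State how the first arm was chosen and whether alternation ran separately by sex. Report each group's start date and order by arm. If a random draw did fix the first arm, document it and state that later groups were predictable.
3. **Objective and estimates.** Reword Aim 1 objective 4 as comparability of the arms under alternation. Attach the same allocation label to the β3 result and to the effect size carried to the full RCT.

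The cost is wording changes, an ethics amendment, possibly one sealed draw, and a less favourable design label. No participants, visits or waiting time are added. The men's allocation, and what screened participants were already told, cannot be changed.

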Data will be analyzed using Statistical Applications Software (SAS) or the Statistical Package for the Social Sciences (SPSS). If software is not available locally, coded data (the code being the participant’s study ID number) will be housed at VA Informatics and Computing Interface (VINCI; <http://vaww.vinci.med.va.gov/vincicentral/VINCIWorkspace.aspx>) in order to access their data analysis software. The VA Informatics and Computing Infrastructure is a partnership between the VA Office of Information Technology and the Veterans’ Health Administration Office of Research and Development. Our researchers and operations staff can use VINCI to access data and statistical analysis tools in a virtual working environment through a certified VHA network computer using the VA Intranet or Virtual Private Network (VPN). VINCI will be used primarily to provide our investigators with the opportunity to use statistical software packages that are not available locally.

Staff members who leave the research project will have access to all research data removed immediately (e.g., permissions to the research folders on the shared drive revoked). Any issues involving potential privacy or confidentiality violations or problems will be reported to the facility’s Information Security Officer(s) and Privacy Officer immediately.

With regards to the videorecordings taken during treatment sessions, we will videotape all counseling sessions using a VA-approved videorecording device, the Toshiba Camileo x200. Recordings will be moved from the camera to the VA shared drive, S:\Nicotine Research\Study Information\Study Logbooks\gCBT for An.Agg\Therapy Recordings. These recordings will be retained according to the VA Records Control Schedule.

Data Analysis and Statistical Considerations

Intention-to-treat random-effects mixed regression models will be used to analyze treatment effects. Changes in aggression across time will be modeled as a function of treatment group (CBT-A vs. PCT), time

(within-subject repeated measures), and the interaction of group x time. Mixed effects models with random intercepts will account for subject effects and correlation of repeated measures over time. Models will be developed that include as independent variables the treatment group and baseline aggression score. The effect CBT-A (vs. PCT) will be assessed by examining the significance of the slope β_3 in the following model:

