$$A_{ik} = \beta_0 + \beta_1 t_{ik} + \beta_2 x_i + \beta_3 (x_i \times t_{ik}) + v_{0i} + v_{1i} t_{ik} + \epsilon_{ik}$$

Where A_{ik} is the aggression score for the i^{th} participant at time point k ; β_0 is the aggression score at baseline; x_i is the dummy-coded treatment group variable ($x_i=0$ for PCT and $x_i=1$ for CBT-A); β_1 is the linear effect of time for the PCT group; β_2 is the condition difference at baseline; β_3 is the condition difference in terms of the linear effect over time; v_{0i} and v_{1i} are subject-specific random effects representing the deviation of each subject from the group intercept and linear trend; and ϵ_{ik} is random residual effects (Hedeker & Gibbons, 1997).

Mixed models are able to handle missing data. Pattern mixture models can be used to describe the effects of missing data on outcome and to provide estimates by averaging over missing data (Hedeker & Gibbons, 1997); and Intent to Attend the next session data can be used to determine if participant drop-out or loss to follow-up meets the assumption of ignorable attrition (Leon, Demirtas, & Hedeker, 2007).

Power Analysis and Sample Size Determination

The paucity of studies examining outcomes of treatment for anger and aggression in Veterans with PTSD, and the inconsistency in measures used across studies, makes it difficult to estimate effect size for sample size estimations. One study reported pre- to post-treatment decreases in aggression with an effect size in the medium range (Marshall, et al., 2010). This is consistent with more general studies of anger management therapies, where effect sizes have been reported in the medium to large range depending upon the measure used and the population sampled (Del Vecchio & O'Leary, 2004; DiGiuseppe & Tafrate, 2003).

Effect sizes for sample size determination of the larger RCT will be calculated based on differences between pre-treatment and post-treatment scores on the measures of aggressive behavior. Comparisons will be made using a two-sample t-test. Because there is a risk of inaccurate estimation of effect sizes in pilot studies (Kraemer, 1992), we will employ recommended procedures for improved characterization of effect sizes derived from pilot studies. These include close consultation with clinicians who have used the treatment (i.e. [name]), and accounting for the effect size uncertainty by constructing confidence intervals around the observed effect sizes.

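### The effect size meant to size the full RCT comes from an unadjusted pre-post t-test, which matches neither the planned mixed-model analysis nor the commitment to analyse all 36 participants

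*Combined protocol and SAP*

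**What the plan says.** The Power Analysis and Sample Size Determination section states: "Effect sizes for sample size determination of the larger RCT will be calculated based on differences between pre-treatment and post-treatment scores". The next sentence is: "Comparisons will be made using a two-sample t-test". For this step it names no covariate, no rule for a missing post-treatment score and no SD for standardizing.

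Other parts of the plan describe something different:

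- Subject Recruitment says the full RCT will use an intent-to-treat, mixed-model repeated-measures analysis, and of the pilot: "we will include all 36 randomized participants in all analyses". The same paragraph assumes 15% drop-out, leaving 30 who complete the interventions.
- Data Analysis and Statistical Considerations says "Intention-to-treat random-effects mixed regression models will be used to analyze treatment effects". It adds: "Models will be developed that include as independent variables the treatment group and baseline aggression score".
- The equation printed in that section tests β3, which "is the condition difference in terms of the linear effect over time". Per the assessment table in Measures, the aggression measures are taken at pre-treatment, post-treatment, 3 months and 6 months.
- Screening Procedures says groups start once six people are enrolled, alternating between CBT-A and PCT, and that covariates will be used if randomization appears to have failed.

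**The concern.** The estimate carried into the design of the next trial is produced by a method that trial will not use. There are three consequences.

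First, a change score exists only when both scores exist, so the step cannot include everyone randomized unless every post score is obtained. It also bypasses the mixed model on which the plan relies for missing data.

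Second, subtracting the baseline is a less precise way to use it than adjusting for it whenever the pre-post correlation is below 1. A t-test also cannot carry the covariates promised for imbalance.

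Third, a pre-to-post difference and a linear slope over four visits are different quantities, and one does not convert into the other without knowing the trajectory.

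What is at stake is the effect size, and its uncertainty, handed to the RCT.

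**Working it through.** **Inputs from the documents.** 36 randomized, 18 per arm (end of Background and Significance); 15% drop-out and 30 completers (Subject Recruitment); visits as listed above.

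**Assumed, because the documents give no figure.** d = 0.5, pre-post correlation r = 0.3 to 0.8, equal pre and post variances, and independent participants. The last ignores therapy-group clustering, so the intervals below are if anything too narrow.

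**The plan's own figure.** 36 × (1 − 0.15) = 30.6, stated as 30. It reproduces, but it counts people who finish treatment, not people with a post score.

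**1. Missing post scores.** Approximate 95% half-width for d with n per arm: 1.96 × √(2/n + d²/(4n)).

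- n = 18: 1.96 × √(0.1111 + 0.0035) = 0.66
- n = 15: 1.96 × √(0.1333 + 0.0042) = 0.73

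The noncentral-t intervals agree: −0.17 to 1.16 with 18 per arm and −0.23 to 1.22 with 15. The n = 15 case applies only if six people lack a post score, split evenly between arms. The true number could be zero or more than six.

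**2. Precision.** In units of the raw-score variance, each participant contributes 2(1 − r) to the change-score variance and 1 − r² to the baseline-adjusted variance. The ratio is (1 − r²)/(2(1 − r)) = (1 + r)/2.

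| r | Change score, 2(1 − r) | Adjusted, 1 − r² | Ratio |
|---|---|---|---|
| 0.3 | 1.40 | 0.91 | 0.65 |
| 0.5 | 1.00 | 0.75 | 0.75 |
| 0.7 | 0.60 | 0.51 | 0.85 |
| 0.8 | 0.40 | 0.36 | 0.90 |

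**3. Scale.** The standardizing SD is not stated. A difference of 0.5 baseline SDs equals 0.5/√(2(1 − r)) change SDs: 0.42, 0.50 and 0.65 at r = 0.3, 0.5 and 0.7.

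**4. Target quantity.** Put the visits at months 0, 3, 6 and 9 (12 weeks of treatment, then 3 and 6 months). The centred times are −4.5, −1.5, 1.5 and 4.5, with sum of squares S = 45. Let D be the arm difference at post-treatment and b the fitted slope difference per month. With a random intercept only (a simplification, since the printed equation also has a random slope), N for the slope test relative to the change-score test is (D²/2)/(b²S).

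- Difference appears at post and is kept: b = 4.5D/45 = 0.1D, ratio 0.5/0.45 = 1.11.
- Half of it is lost by 6 months: b = 1.875D/45 = 0.0417D, ratio 0.5/0.0781 = 6.4.
- It keeps growing linearly: b = D/3, ratio 0.5/5 = 0.1.

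The change-score figure could therefore make the RCT far too small or far too large for a slope test.

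**The case against.** **Dropping people is inferred, not stated.** A reader might conclude that the plan discards six participants. It does not say so. It says all 36 are analysed, and Aim 1 lists group drop-out and assessment retention as separate objectives. This stands: the number without a post score is unknown. What remains is that the named method cannot deliver the all-36 commitment unless every post score is obtained.

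**The printed model is not baseline-adjusted either.** It treats baseline as an outcome with a free arm difference (β2). With two complete time points its β3 equals the change-score difference. This also stands. On adjustment, the conflict is with the sentence naming baseline as an independent variable, which itself disagrees with the equation. On time points and missing data, the conflict is with the equation.

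**Starting whole groups alternately weakens the case for adjustment.** If the arms differed in stable level by g, a baseline-adjusted estimate would be off by (1 − r)g and the change score would not. If the gap is chance imbalance, the reverse holds: one standard error at 18 per arm is √(2/18) = 0.33 SD, which at r = 0.5 shifts the change score by 0.17 SD. This limits the precision claim. It does not rescue the t-test as the sole estimator, because the plan calls the trial randomized and promises covariates that a t-test cannot carry.

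**The plan already concedes that pilot effect sizes are unreliable.** It proposes clinician consultation and "accounting for the effect size uncertainty by constructing confidence intervals around the observed effect sizes". These are sound, but they leave the estimator unchanged. At d = 0.5 the interval spans zero with either 15 or 18 per arm, so no estimator makes this pilot's effect size precise.

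**Conclusion.** The mismatch is real and should be corrected. The sizing step uses an unadjusted change-score t-test, while the plan elsewhere specifies a mixed model, all 36 participants and a baseline term.

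The effect of missing scores is modest: about 0.07 on the half-width if six post scores are missing. The precision loss is 10% to 35% of the variance over r = 0.3 to 0.8, assuming equal variances and arms comparable at baseline. The difference in target quantity could matter most, but it cannot be sized without the trajectory.

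A reader might infer that the t-test inflates the RCT's sample size by a fixed amount, for example one third at r = 0.5 (1/0.75 = 1.33). The documents do not support this. It presumes an RCT analysed by baseline-adjusted comparison at a known r, whereas no r is given and the only printed model tests a slope, for which the error can run either way.

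Nor is this effect size the pilot's central output: Aim 1 is feasibility, with seven objectives. The pilot's N of 36 and its own mixed-model analysis are untouched.

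**What to change.** In Power Analysis and Sample Size Determination, replace the t-test as the source of the effect size with the post-treatment arm contrast from a likelihood-based repeated-measures model. Use categorical time, and treat the baseline score as an outcome whose mean is constrained to be equal across arms. All 36 then contribute, although someone with only a baseline score adds little to the contrast. Entering baseline as an ordinary covariate would still lose anyone with no later score.

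Standardize by the pooled baseline SD, and report the pre-post correlation and a 95% CI. State that the correlation enters the RCT formula, for example n per arm = 2(z₁₋α/₂ + z₁₋β)²(1 − r²)/d². Without that step the precision gain is not carried over. This formula suits an RCT whose primary contrast is the same post-treatment difference; one that keeps the linear slope must be sized on the slope.

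Keep the change-score t-test as a descriptive sensitivity check, which is useful given the alternating group starts. Reconcile the baseline-covariate sentence in Data Analysis and Statistical Considerations with the printed equation.

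Cost: no new data, since both scores are already scheduled. A somewhat different model must be specified, and the constrained baseline relies on the arms being comparable at entry.
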